The Role of Acetazolamide in Mitigating Inflammation and Innate Immune Activation at High Altitude

Date of document: September 27, 2024

Title of Project: The role of acetazolamide in mitigating innate immune activation at high altitude: a randomized cross-over controlled trial

Executive Summary: High altitude exposure can lead to an acute pro-inflammatory response and activation of innate immune cells.¹⁻⁶ Our prior work demonstrates that 1 to 3 days at 3800 m elevation leads to increased expression of inflammatory damage associated molecular patterns (DAMPs), several toll-like receptor pathways involved in innate immune responses, as well as increases in pro-inflammatory monocyte and neutrophil subpopulations.^{1,6,7} Furthermore, our data and others indicate that either hypoxia-induced inflammatory responses, or baseline immune parameters, likely play a role in the onset and severity of Acute Mountain Sickness (AMS), although the precise mechanism is unknown.⁷ One of the most effective medical treatments for AMS is Acetazolamide (AZ).⁸ The mechanism of action by which AZ alleviates AMS is through regulation of blood bicarbonate levels, modification of blood pH, and resulting increases in ventilation and improved tissue oxygenation.⁸⁻¹⁰ However, AZ is also reported to have anti-inflammatory and immune-modulatory properties in animal models, which have not been evaluated as a potential mechanism of action in AMS treatment.^{11,12} We hypothesize that AZ will reduce pro-inflammatory responses and innate immune activation during 3 days of high-altitude exposure. To test this hypothesis, we will conduct a randomized, cross-over, placebo-controlled trial in which we administer AZ or placebo treatments to N=20 individuals over two visits to 3800 m elevation. Outcome measures will include the most detailed evaluation of systemic inflammatory and immune parameters to date in this field, as well as contributing physiological parameters including ventilatory chemoreflex sensitivity, and daytime and nocturnal pulse oximetry. This work will advance our knowledge about the pathology and treatment of a key wilderness medicine challenge by identifying a potential novel mechanism of AMS onset and treatment.

Section I – Summary

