A. Introduction and Background: Acetazolamide (AZ) is a highly effective treatment for acute mountain sickness (AMS) at high altitude.^{8,9} AZ mitigates AMS through its activity as a renal carbonic anhydrase inhibitor, which decreases blood pH and stimulates ventilation to improve oxygen delivery to tissue.^{9,10} However, AZ also demonstrates immune modulatory properties, with most evidence examining this in lung tissue to investigate the impact on pulmonary hypertension in animal models.^{11,13} Our group and others show that high-altitude exposure results in an acute pro-inflammatory response and activation of the innate immune system, which some predict contributes to the onset and severity of AMS.^{1,7} Therefore, the anti-inflammatory properties of AZ may play a key role in modulating AMS symptoms independent of ventilatory stimulation. However, prior work has examined the impact of AZ on only a select few inflammatory mediators, and the impact of AZ on immune function has never been evaluated.

B. Hypothesis and specific aims: Our goal is to determine if AZ mitigates the pro-inflammatory innate immune response during high altitude travel. We hypothesize that AZ improves AMS symptoms, in part, by reducing systemic hypoxia-induced inflammation and reducing the activation of innate immune cells (monocytes and neutrophils). We will test this hypothesis with the following experimental aims: (**Aim 1**) Determine if AZ treatment during high altitude exposure blunts plasma inflammatory cytokine expression and levels of circulating pro-inflammatory innate immune cell subsets; (**Aim 2**) Determine if AZ treatment during high altitude exposure modulates immune cell function (innate inflammatory responses to bacterial and viral stimuli, cell migration, and bacterial killing efficacy).

C. Study design and methods:

a. Study Design: This is a double blind, randomized, cross-over, placebo-controlled trial.

Participants (N=20) will be recruited by word of mouth and advertising, and complete written

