informed consent in the UC Riverside laboratory within 1 month of first ascent (Summer 2025). Participants then complete medical history and basic physical screening. At this time, they are randomly assigned to a treatment group (*i.e.* Group A taking AZ on trip 1 and placebo on trip 2), maintaining age and sex ratios across groups. Participants will be asked to begin taking their assigned treatment as indicated 2 days before each ascent (125 mg twice daily for AZ).¹⁴ On the morning of ascent, participants arrive at the lab at 6:00 am and fasting peripheral venous blood samples will be collected by a licensed phlebotomist or physician. Participants then travel to Barcroft Station (3800 m elevation) *via* vehicle (6 -7 hours). Over three days at high altitude, participants complete morning fasting blood draws, morning and evening AMS questionnaires (Lake Louise)¹⁵, and morning and evening physiological measures (blood pressure, heart rate, SpO₂). On the second day at high altitude, ventilatory chemoreflex measures will be collected as previously described by our group.¹⁶ WatchPAT sleep kits will be used to characterize nocturnal hypoxic burdens, oxygen desaturation indices, and apnea hypopnea indices as previously described by our group.¹⁷ Following descent, participants complete 1-week and 1-month follow-up visits to determine the long-term effects of high-altitude exposure on immune phenotypes.

100 µl of whole blood will be fixed and stained immediately on-site at each timepoint for flow cytometry analysis at UC Riverside within 3 days of sample collection. We will also conduct complete blood counts on-site. 20 ml of EDTA-treated blood will be utilized for plasma collection and isolation of peripheral blood mononuclear cells by density gradient centrifugation. Isolated immune cells will be immediately frozen and stored in liquid nitrogen for transport to UC Riverside using a novel protocol optimized by our group for cryogenically storing viable cells in remote field locations.⁷ Upon return to sea level, immune cells will be cultured in the presence or absence of several stimulants including bacterial lipopolysaccharide (LPS) and R848 (Resiquimod, stimulating the antiviral response). Following stimulation, we will collect culture

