innate immune cell subsets (Aim 1), we will first utilize two-way repeated measures ANOVA to compare plasma cytokine expression and cell distributions across study days and treatments. To determine the impact of AZ treatment on innate immune cell function (Aim 2), we will use a three-way ANOVA to examine cell cytokine secretion across study days, treatments, and pre/post cell stimulation. Significant main effects will be further evaluated with post-hoc Tukey's HSD tests, and we will verify our data meets all required test assumptions. We will carefully examine impacts of sex, age, BMI and other demographic factors on outcomes using mixed linear models. WatchPAT data will be analyzed according to the American Academy of Sleep Medicine criteria by a qualified sleep technician and ventilatory parameters will be analyzed as described previously.^{16,20–22} To determine if these parameters are associated with our immune and AMS outcomes, we will conduct mixed linear models with trip, day, treatment, and sex, as covariates.

d. Timeframe: This study will take place in the summer of 2025. Participants will be recruited in the month prior to study start, and work will be conducted over two expeditions. Participants will complete baseline testing within one week of ascent. They will then arrive on the morning of ascent for sea-level blood sampling, be driven to Barcroft Station over 6 hours in vans, and will remain at the station for 3 nights (4 days) during each visit. The group will then return to sea level and a follow-up appointment will be completed 1 week and 1 month following return. The second trip will take place 1-2 months after the first. Flow cytometry and multiplex cytokine panel tests will be conducted immediately after each trip, and cell functional assays will be completed within 2 months of return. Final data analyses will be complete over the following 2 months in time for an abstract submission to the American Physiology Summit by the deadline in Fall 2025 and attendance of the 2026 Winter Conference of the Wilderness Medical Society. The manuscript resulting from this work will be submitted for publication in *Wilderness & Environmental Medicine* by Summer 2026.

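### The post-hoc rule is triggered by main effects, whereas the hypothesis is an acetazolamide effect at altitude, and no treatment-by-day or altitude-day contrast is named

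*Protocol*

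**What the plan says.** The Executive Summary places the expected effect at altitude: "We hypothesize that AZ will reduce pro-inflammatory responses and innate immune activation during 3 days of high-altitude exposure". Section I.B gives the mechanism as acting "by reducing systemic hypoxia-induced inflammation and reducing the activation of innate immune cells", and Aim 1 reads "Determine if AZ treatment during high altitude exposure blunts plasma inflammatory cytokine expression". Aim 2 uses the same altitude framing for immune cell function.

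For Aim 1, Section I.C.c (Data analysis plan) says "we will first utilize two-way repeated measures ANOVA to compare plasma cytokine expression and cell distributions across study days and treatments". Aim 2 gets a three-way ANOVA that adds pre/post stimulation as a factor. The only follow-up rule is "Significant main effects will be further evaluated with post-hoc" Tukey HSD tests. No interaction term, altitude-day contrast or change from sea level is named as the test of AZ.

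Section I.C.a (Study Design) and Section I.C.d (Timeframe) describe, for each trip, one sea-level blood sample on the morning of ascent, fasting morning draws over three days at altitude, and two later visits: "Following descent, participants complete 1-week and 1-month follow-up visits". The Protocol does not say which of these make up the study-day factor.

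**The concern.** The quantity of interest is the AZ-minus-placebo difference on the altitude days. Neither main effect is that quantity. A significant day effect, which the group's earlier altitude data lead one to expect, would trigger Tukey tests without any evidence about AZ. The treatment effect averages the AZ-placebo difference over every day in the factor, including a day without the hypoxia that the mechanism requires. In Aim 2 it also averages over unstimulated cells.

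So the test that decides whether AZ is examined further loses power when AZ works as hypothesised. With 20 participants, a missed main effect could be reported as AZ not modulating inflammation. The power section gives no reserve against this: it addresses sea level versus altitude, and correlations with AMS score, but not the treatment comparison.

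**Working it through.** **The plan's own figure.** Section I.C.b gives n=14 for an effect size of 0.46 at 80% power and alpha 0.05. A one-way ANOVA with f=0.46 and four levels gives 13.90, hence 14. Four levels is an inference; sea level plus three altitude days would fit. A paired t-test with d=0.46 would need 40 (two-sided). On the reading that reproduces it, the figure concerns a day effect and says nothing about AZ.

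**Inputs.** From the Protocol: N=20 in a cross-over, alpha 0.05, one sea-level sample, three altitude mornings and two follow-up visits per trip. Assumed: a two-sided test, complete data, and AZ-minus-placebo differences with unit variance on each day and a common correlation ρ between days. The Protocol does not give ρ, so a range is shown. ρ is the share of the variance of the daily difference that is person-by-treatment.

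**Formulas.**
- Variance of a participant's mean difference over K days: V(K) = [1 + (K−1)ρ]/K.
- Power = P(|T| > 2.093), where T is noncentral t with 19 df and noncentrality √20 × mean/√V.
- 80% power needs mean/√V = 0.660, so the altitude effect is set at δ = 0.660 × √V(3).
- With effect δ on three altitude days and none elsewhere, the treatment main effect is 3δ/4 = 0.75δ over four days and 3δ/6 = 0.50δ over six.
- With half the effect at sea level, the four-day main effect is (3 + 0.5)δ/4 = 0.875δ.

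**Worked case, ρ = 0.5.** V(3) = 2/3, so δ = 0.660 × 0.816 = 0.539. V(4) = 0.625, with square root 0.791. The standardised main effect is 0.75 × 0.539/0.791 = 0.51, which gives 58% power.

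**Power of the treatment main effect when the altitude contrast has 80%:**

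| ρ | δ | 4 days, no sea-level effect | 4 days, half effect at sea level | 6 days, altitude effect only |
|---|---|---|---|---|
| 0 | 0.381 | 68% | 81% | 51% |
| 0.3 | 0.482 | 61% | 74% | 36% |
| 0.5 | 0.539 | 58% | 72% | 32% |
| 0.7 | 0.591 | 57% | 70% | 31% |
| 0.8 | 0.615 | 57% | 70% | 30% |

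**The interaction test.** In 20,000 simulated trials per setting, four days, altitude-only effect, ρ = 0 / 0.3 / 0.5 / 0.7:
- Power of the omnibus treatment-by-day F test: 20% / 41% / 66% / 94%.
- Interaction significant but treatment main effect not: 6% / 16% / 27% / 40% of trials.

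**The reverse case.** If AZ acts equally on all four days, V(4) replaces V(3) with the full δ. The main effect then has 81% to 90% power against 80% for the altitude contrast.

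**The case against.** The strongest reply is that the rule does not say that only main effects count. A factorial ANOVA normally reports the interaction, nothing forbids testing it, and contrast definitions are often left to a statistical analysis plan, which is not shown here. This stands in part: a reader might infer that the interaction is excluded, and the text does not say so. But the Protocol does state a follow-up rule, and that rule omits the comparison that the hypothesis calls for. Turning to an interaction after seeing the data, across the many analytes of Section I.C.a, would be unplanned.

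It can also be said that the interaction is not a better test in general. That is right: with four days and ρ of 0 to 0.3 it has 20% to 41% power, below the main effect's 61% to 68%. This argues for an altitude-day contrast, not for the main effect.

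Two stronger readings are tempting, and the documents do not support them.
- **That off-drug follow-up days halve the effect.** The Protocol says neither when dosing ends nor that the 1-week and 1-month visits enter the day factor. It gives those visits their own purpose, long-term effects, and the reproduced n=14 would fit a four-level factor.
- **That AZ has no valid baseline.** Participants "begin taking their assigned treatment as indicated 2 days before each ascent", and "They will then arrive on the morning of ascent for sea-level blood sampling", so that sample is on study drug. But no change-from-sea-level score is planned. The timeframe also mentions baseline testing within a week of ascent without giving its content. The argument also pulls against the dilution argument: an AZ effect already present at sea level makes the dilution smaller.

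**Conclusion.** The point holds in a limited form. As written, the follow-up rule does not test the stated hypothesis. If AZ has no effect at sea level, the treatment main effect over four sampling days carries 75% of the altitude effect, and 80% power becomes about 57% to 68%. If half the effect is present at sea level, power is about 70% to 81%, so at low correlation the loss disappears. The fall to 50% of the effect and about 30% to 51% power applies only if both follow-up visits are in the day factor, which is not stated.

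These figures rest on a two-sided 0.05 test, complete data on 20 participants, equal variances and correlations across days, and an assumed ρ. How often a real AZ effect would be missed in practice is therefore unknown. The mismatch between rule and hypothesis does not depend on these assumptions.

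**What to change.** In Section I.C.c, replace the main-effect trigger as follows.
- **Aim 1:** the test of AZ is a prespecified AZ-minus-placebo contrast averaged over the three altitude mornings, taken from the repeated-measures or mixed model. Report treatment-by-day as supporting evidence.
- **Aim 2:** use the same altitude-day contrast in stimulated cells.
- **Follow-up visits:** keep the 1-week and 1-month samples out of this contrast and analyse them separately.
- **Day-specific AZ-placebo contrasts:** make them secondary, with multiplicity control, since they add three tests per outcome.

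The cost is wording only, with no new samples, visits or participants; it should be settled before unblinding. The downside is a little lost precision if AZ acts equally on all days including sea level: 80% power against 81% to 90% for the four-day main effect.

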supernatants and measure expression of inflammatory factors using Legendplex multi-plex cytokine panels as previously described by our group.¹⁸ These panels allow simultaneous measurement of many key inflammatory mediators including 13 inflammatory cytokines, 12 markers of vascular inflammation, and 13 anti-viral response factors. We will also conduct additional functional assays, including bacterial killing and cell migration assays. Plasma cytokine levels will also be measured via Legendplex. All cell culture assays will be conducted in triplicate with downstream cytokine profiling in duplicate.

b. Power calculations: Sample sizes are based on power calculations targeting 80% power to detect significant differences across sea level and high altitude at $\alpha = 0.05$. Calculations were performed using *pwr* in R and are based on previously published data or our own preliminary work. A sample size of 14 is required to detect a significant shift from classical to intermediate monocyte subsets after 1 day at high altitude with an effect size in our prior studies of 0.46.⁷ Additionally, a sample size of 10-36 is required to detect significant correlations between AMS score and classical ($R^2 = 0.79$) or non-classical monocytes ($R^2 = 0.45$). Finally, we previously identified elevations in inflammatory response genes after 1-3 days at high altitude with a sample size of 17.¹ Thus, we predict we are well powered with a sample size of 20 individuals (cross-over design) to detect significant changes in immune phenotypes at high altitude as well as correlations between immune cell distributions and AMS scores. This sample size is also consistent with other studies examining the efficacy of AZ for AMS treatment.¹⁹

c. Data analysis plan: Treatments will be assigned by a third party and all study team members and participants will be blinded. Data analysis will be conducted by a research team member who is blinded to participant treatment, demographic information, and day of sample collection. All samples and physiological data will be deidentified and coded. To determine if AZ treatment is linked to reduced inflammatory cytokine expression and reduced levels of pro-inflammatory

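### At the short end of the 1-2 month gap between trips, the trip-1 one-month follow-up falls on or after the start of trip-2 treatment

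*Protocol*

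**What the plan says.** The schedule is spread over two parts of Section I of the protocol.

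- **C.d Timeframe, spacing of trips:** "The second trip will take place 1-2 months after the first". What the gap is counted from (ascent or return) is not stated.
- **C.d Timeframe, length of stay:** participants "will remain at the station for 3 nights (4 days) during each visit".
- **C.d Timeframe, follow-up:** "a follow-up appointment will be completed 1 week and 1 month following return". No visit window is given.
- **C.a Study Design, treatment start:** "Participants will be asked to begin taking their assigned treatment as indicated 2 days before each ascent".
- **C.a Study Design, cross-over:** the example sequence is "Group A taking AZ on trip 1 and placebo on trip 2", so each participant takes the other treatment on the second trip.
- **C.a Study Design, purpose of the follow-up visits:** "to determine the long-term effects of high-altitude exposure on immune phenotypes".

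Nothing in the protocol requires the trip-1 one-month visit to be finished before trip-2 treatment begins.

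**The concern.** The follow-up is counted from return, which is three days after ascent, and trip-2 treatment begins two days before the second ascent. A gap of one month therefore leaves no room for a visit one month after return that is still free of the second period.

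A sample drawn then would not show the late effect of the first trip alone. Depending on the date, it would also reflect trip-2 drug, or a second altitude exposure. The trip-2 one-month samples have no third period after them, so the two sets would not be comparable. The trip-1 visit is also the latest scheduled follow-up that could show whether first-period immune changes had resolved before the second period.

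The short end of the range is a realistic choice. C.d places both expeditions in one summer, allows up to two months for functional assays and two more for analysis, and aims for an abstract deadline in the fall. That timetable favours an early second trip.

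**Working it through.** The protocol gives no derived figure to reproduce here, so the check is a day count on its own schedule.

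**Inputs**
- First ascent = day 0. Stay of 3 nights, so return = day 3 (C.d).
- One-month visit = day 3 + M, where M is the length of a month in days. M = 30 is an assumption, varied below (C.d).
- Trip-2 treatment start = A − 2, where A is the day of the second ascent (C.a).
- 20 participants × 2 trips = 40 planned one-month samples, 20 of them after trip 1. This assumes follow-up after each trip, and that all participants travel on the same dates, as the two expeditions in C.d suggest.

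**Condition for a clean visit**

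The visit must come strictly before treatment start: 3 + M < A − 2, so A ≥ M + 6. With M = 30 the visit is on day 33 and A must be at least 36.

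**Permitted second ascents that clash (M = 30)**

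| Gap counted from | Permitted A | Clashing A | Share of permitted days |
|---|---|---|---|
| Ascent to ascent | 30-60 | 30-35 | 6/31 = 19% |
| Return to ascent | 33-63 | 33-35 | 3/31 = 10% |
| Return to first dose | 35-65 | 35 | 1/31 = 3% |

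The lower limit clashes under each way of counting, and the two-month end never does.

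**What the day-33 sample would contain**
- A = 30: treatment starts on day 28, and the visit falls on the day of return from the second stay. All 20 trip-1 samples follow new altitude exposure: 20/40 = 50%.
- A = 31 or 32: participants are at the station on day 33, so a sea-level visit cannot take place on that day. It is moved or missed.
- A = 33: treatment starts on day 31, and the visit falls on ascent morning after two days of treatment, before new altitude exposure.
- A = 34: treatment starts on day 32, and the visit falls one day into treatment.
- A = 35: the visit falls on the day of the first dose. It is clean only if blood is drawn before that dose.

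For A = 33 to 35, only those assigned acetazolamide on trip 2 can carry active drug. With equal sequence groups, which the protocol does not state, that is 20/2 = 10 of 40 samples (25%).

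**Sensitivity to the length of a month**

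The minimum clean gap is M + 6 days ascent to ascent, or M + 6 − 3 = M + 3 days return to ascent. For M = 28, 30 and 31 this gives 34, 36 and 37 days, or 31, 33 and 34 days. A visit allowed to run w days late adds w to each.

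**The case against.** The strongest reply is that the passages do not contradict each other over most of the window. Both timings can be met on 25 to 30 of the 31 permitted days, depending on the anchor. The figures are round planning numbers in a document written before funding, with no expedition dates. C.d also mentions the follow-up visits before the second trip, which fits an intended order. Visit windows and the handling of mistimed samples may be set elsewhere. Most of this stands as a limit on size. It does not remove the problem: the protocol itself sets the spacing, its permitted minimum fails under each way of counting, and no analysis rule can recover a clean sample that was never drawn.

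Three stronger readings are tempting, and the documents do not support them.

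- A reader might infer that any short gap puts half of all one-month samples under the wrong treatment. That is the maximum and needs the second ascent to precede the visit. Otherwise those on placebo in trip 2 have neither active drug nor new altitude exposure, so the contamination is one-sided by sequence.
- A reader might infer that no clean check of resolution before period 2 would remain. The one-week visit, on about day 10, precedes trip-2 treatment under every anchor. It is early, but clean.
- A reader might infer that the main treatment comparison is compromised. Aims 1 and 2 concern responses during altitude exposure, and the power calculation in C.b does not use the one-month sample.

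**Conclusion.** The concern holds, within limits. The lower end of the stated gap is incompatible with a clean trip-1 visit one month after return, and nothing in the protocol fixes the order. With a 30-day month, second ascents on days 30-35 after the first clash if the gap is counted ascent to ascent, and on days 33-35 if counted return to ascent. Later dates are clean.

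The loss ranges from about 10 of 40 one-month samples carrying active drug (equal sequences assumed) to all 20 trip-1 samples affected by new altitude exposure, or the visit moved or missed. The harm is to the long-term follow-up comparison and to the latest check for resolution before period 2. The on-altitude comparisons are not directly affected. The conclusion rests on follow-up after each trip, shared expedition dates, and a visit held at its nominal time.

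**What to change.** Reconcile C.a and C.d in three steps.

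1. State what the gap between trips is counted from.
2. Require the trip-1 one-month blood draw to be completed before the first trip-2 dose.
3. Raise the lower bound of the gap so that this order is guaranteed: at least about 36 days ascent to ascent, or 33 days return to ascent, plus any tolerance allowed for the visit. The two-month upper limit can stay.

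With these changes the affected samples fall from up to 20 of 40 to none. The cost is slightly less freedom in choosing the second expedition date. Before any visit tolerance, and with a 30-day month, 25 of the 31 permitted days remain if the gap is counted ascent to ascent (36-60), and 28 of 31 if counted return to ascent (33-60).

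### Cytokine panels run after each trip put every participant's acetazolamide and placebo plasma in different assay runs, and the Aim 1 ANOVA has no trip or plate term, which costs precision

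*Protocol*

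**What the plan says.** Protocol Section C.d (Timeframe) fixes when the assays are run: "Flow cytometry and multiplex cytokine panel tests will be conducted immediately after each trip". It also says "The second trip will take place 1-2 months after the first". Section C.a gives the cross-over allocation, for example "Group A taking AZ on trip 1 and placebo on trip 2", and says of the plasma "Plasma cytokine levels will also be measured via Legendplex". Plasma cytokines are an Aim 1 outcome (Section B).

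Section C.c analyses them with a two-way repeated measures ANOVA whose factors are study day and treatment. Trip appears only later in that section, as a covariate in the mixed models that relate the sleep and ventilatory measures to the immune and AMS outcomes. The protocol describes no plate layout, bridging sample or plate term.

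**The concern.** The cross-over is used so that each person is their own control. Here the AZ-minus-placebo difference within a person is always a trip 1 versus trip 2 difference. With panels run trip by trip, it is also always a run 1 versus run 2 difference. Calibration shifts between runs, and differences between plates within a run, are therefore added to the one contrast the design is meant to sharpen. The stated Aim 1 model has no term to take them out.

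At stake is power in a 20-person trial. The assay schedule also cannot be undone later: once trip-1 plasma has been assayed alone, analysis can remove an average shift but cannot put both treatments on one plate.

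**Working it through.** **The plan's own figures.** The stated N of 14, "with an effect size in our prior studies of 0.46", is reproduced by a one-way ANOVA calculation with f = 0.46 and four groups (power 0.803). It concerns sea level versus altitude, not AZ versus placebo, so it neither contains nor depends on assay error between trips. The check below therefore starts from a reference effect chosen to give 80% power.

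**Inputs.**
- From the protocol: n = 20, cross-over; alpha 0.05; 80% power; one sea-level draw and three altitude draws per trip.
- Assumed: two-sided test; 10 participants per sequence; assay error additive on the analysis scale; the sizes of the run and plate errors.
- Unit: the SD of the paired difference is 1.

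**Base.** Paired t-test with standardised effect d = 0.66 and n = 20: noncentrality 0.66 × √20 = 2.95, 19 df, power 0.799.

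**Trip-wide shift π, no trip term (the stated ANOVA).** The shift adds +π to the AZ-minus-placebo difference in one sequence and −π in the other. It cancels from the mean but inflates the residual variance to about 1 + π², so the effective d is 0.66/√(1 + π²).

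| π (SD) | Effective d | Power, formula | Power, simulated | Simulated with trip term |
|---|---|---|---|---|
| 0.25 | 0.640 | 0.775 | 0.781 | 0.797 |
| 0.5 | 0.590 | 0.707 | 0.722 | 0.797 |
| 1.0 | 0.467 | 0.509 | 0.493 | 0.797 |

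The true sampling error of the estimate is unchanged here; the test becomes conservative. In a separate simulation with run shifts, type I error without the trip term was 0.025 to 0.036.

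**Plate error that remains with a trip term.** Layout: two plates per trip, the same 10 participants grouped together on both trips, sequences balanced within plates. Let r be the variance of a plate group's trip-to-trip difference, as a fraction of the paired-difference variance.

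| r | Trip term only | Trip and plate-group-by-trip terms |
|---|---|---|
| 0.10 | 0.781 | 0.794 |
| 0.25 | 0.755 | 0.794 |
| 0.50 | 0.718 | 0.795 |

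Under a less controlled layout (three plates per trip, participants placed at random each time), power with a trip term was 0.78, 0.74 and 0.60 for a plate SD of 0.25, 0.5 and 1.0 times the within-person SD. With both of a participant's trips on one plate it stayed at about 0.79 to 0.81 throughout.

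**Bias.** With n_A and n_B completers per sequence and no trip term, the estimate shifts by π(n_A − n_B)/(n_A + n_B). This is zero when n_A = n_B. With 10 and 7 completers it is 3/17 = 0.18 of the trip shift. In the balanced simulations bias was at most 0.011.

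**Plates per trip (96 wells, about 80 for samples, assumed).** 20 × 4 = 80 samples: one plate as singlets, two in duplicate. The protocol states duplicates only for cytokine profiling after cell culture ("All cell culture assays will be conducted in triplicate with downstream cytokine profiling in duplicate"), so either is possible for plasma. If both follow-up draws are assayed there are 120 samples: two plates as singlets, three in duplicate.

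**The case against.** Several points on the other side stand.

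- **Size is not in the documents.** No inter-plate variance, plate layout or plasma replication is given. If each trip fits on one plate, a trip term removes an additive shift completely.
- **Much of the loss comes from the model.** The fall to about 78%, 71% or 50% is due to leaving out trip. Real trip differences call for that term whenever the assays are run. Plate terms and bridging controls may sit in an SAP or laboratory manual that is not shown. That answers the missing terms in part, but not the assay schedule, which the protocol itself fixes.
- **The interaction is partly protected.** Aim 1 asks whether AZ blunts the altitude response, which is the day-by-treatment interaction, and each trip has its own sea-level draw. Additive plate error cancels from that interaction if a participant's samples from one trip share a plate. The protocol does not secure that layout.
- **Scope is narrow.** Flow cytometry must be done within 3 days of collection (Section C.a) and cannot be pooled across trips. The timing for culture supernatants is less clear.

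A reader might also infer more than the documents support. One inference is that the AZ effect is biased; that needs both unequal sequences and no trip term. Another is that plate error acts as independent noise for each participant, which would give 76%, 71% and 63%. Plate error is shared by everyone on a plate, so with two plates per trip these figures overstate the loss. A third is that reagent lots must differ between trips; nothing prevents one lot serving both runs.

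**Conclusion.** The point holds as a matter of precision. The schedule in Section C.d guarantees that each participant's AZ and placebo plasma are measured in different runs, and the Aim 1 ANOVA as stated has no term for this. Without a trip term, power falls from about 80% to about 78%, 71% or 50% for trip shifts of 0.25, 0.5 or 1.0 SD of the paired difference; adding trip recovers that. With trip fitted and two plates per trip, plate variance of 10%, 25% or 50% of the paired-difference variance leaves about 78%, 75% or 71%. The loss runs from near zero with one plate per trip to about 20 points in the worst random layout examined.

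All these sizes rest on assumed variances, additive error, a two-sided test and 10 participants per sequence, and they concern the overall AZ-placebo contrast rather than the interaction. The change is a cheap improvement to the design; the present schedule does not invalidate the trial.

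**What to change.** 1. Add trip to the Aim 1 model, whatever is decided about the assays.
2. Amend Section C.d so that trip-1 plasma is held frozen and the plasma panels are run once, after trip 2. Put all of a participant's samples from both trips on the same plate, with AZ-first and placebo-first participants balanced over plates. This must be settled before trip-1 plasma is assayed.
3. If the panels must stay per trip, keep the same participants grouped on plates in both trips, balance the sequences within plates, and fit trip and plate-group-by-trip terms. In the two-plate layout above this holds power at about 79% for one further degree of freedom.
4. Leave flow cytometry per trip.

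**Cost.** Trip-1 cytokine data arrive 1-2 months later. Trip-1 plasma is stored longer than trip-2 plasma, a trip difference that the trip term absorbs. Freezers are listed in Section C.e, although plasma storage itself is not described. With four draws per trip in duplicate and 40 samples per plate, 5 whole participants (8 samples each) fit on a plate, so 4 plates per panel serve either way. If both follow-up draws are also assayed, each participant has 12 samples and 3 fit on a plate, so 7 plates are needed against 6 tightly filled ones: one extra plate per panel.
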